Scientific title

Application of 3D magnetic resonance neurogram sequences for evaluation of Intraparotid facial nerves in patients with parotid neoplasm

Research protocol

Version 4

Date: 6 June 2022

NCT number: NCT05296109

Scientific basis

Parotid neoplasm consists of a wide range of benign and malignant lesions, and parotidectomy has been the mainstay for management of these neoplasms. Within the parotid gland there are branches of the intra-parotid facial nerves, which are tiny in calibre and are prone to injury during operation. It has been reported in recent retrospective reviews that the incidence of temporary and permanent facial nerve injury were 9.2% and 5.2% respectively, the risk of which increased with old age, malignant tumour and revision surgery [1]. Traditionally the incident of facial nerve injury is reduced by intra-operative facial nerve monitoring and surgical magnification, while imaging has limited role in aiding this purpose.

MRI is considered a cornerstone modality in the diagnosis and management of salivary gland tumours, with multi-parametric imaging providing clue to the underlying histology and relationship with adjacent structures. With the advancement of MRI, new and higher resolution three-dimensional sequences such as Dual echo Steady State (DESS) or constructive interference in steady state (CISS) sequences have been shown to better demonstrate the extracranial, intraparotid facial nerves [2-3]. More recent studies have also shown potential use of delineation of facial nerve branches in relationship to tumour [4]. However, the advantages and disadvantages of these sequences remain unknown. Our study aim to compare the efficacy between the two sequences, and also to compare with conventional 3D post-contrast anatomical imaging studies in the localization and visualization of the facial nerve branches in patients with tumour.

Reference:


Study protocol

This study will be a prospective cohort model comparing between the efficacy of different MRI sequences in visualization of the facial nerves.

Patient recruitment

Inclusion: Consecutive patients with parotid tumour diagnosed on other imaging modalities (such as ultrasonography or computed tomography), with or without cytological diagnosis from fine needle aspiration, will be recruited from the ear, nose and throat specialty clinic.

Exclusion:

- Patients who are contraindicated to magnetic resonance imaging (such as due to underlying MRI incompatible metallic implants)
- Patient who are contraindicated to MRI contrast agents (such as advanced renal failure or previous severe allergic reaction)
- Patients who cannot cooperate for MRI scanning.
- Patients show are unable to provide informed consent.

Consent form will be signed by patient before the examination. We currently aim to recruit approximately 50 patients for the purpose of the study according to the following basis for calculation of statistical power.

According to previous studies, there is an estimated ~60% predication of facial nerve with conventional techniques, and ~80% visualization of facial nerves using DESS. With 80% power and two-tail alpha of 0.05, at least 42 patients will be needed according to sample size calculation.

MRI scanning

Patient will be scheduled to be scanned at the Siemens Signa 3T MRI scanner at Gerald Choa Neuroscience Institute, the Chinese University of Hong Kong. The scanning protocol consists of conventional imaging sequences for salivary gland which includes the following sequences:

- Axial T1 weighted spin-echo
- Axial T2 weighted spin-echo (with fat saturation)
- Coronal T2 weighted spin-echo
- Diffusion-weighted imaging.
- Dynamic contrast-enhanced imaging of the salivary gland, with focus on the lesion.
- Axial post-contrast Axial T1 weighted spin-echo
- Axial post-contrast 3D T1-weighted fat-saturated SPACE

In addition, the following sequences will be performed for the purpose of facial nerve mapping:

- 3D Axial Dual-echo steady state sequence.
- Pre-contrast 3D Constructive interference in steady state
- Post-contrast 3D Constructive interference in steady state

Contrast injection will be required for these patients as per usual salivary gland MRI protocol but no additional contrast administration is required for neurogram sequences as these can be performed concomitantly. The whole scanning protocol will take approximately 45 minutes.

Image interpretation

Images will be reviewed by two independent radiologists for the conspicuity of the facial nerves. The intra-parotid facial nerve will be segmented into eight segments, which includes the main trunk (distal to stylomastoid foramen), temporofacial division, cervicofacial division, and five branches (temporal branch, zygomatic, buccal, mandibular, cervical). For each branch, its conspicuity is measured objectively by ratio between the average signal intensity of the nerve as compared to the both the parotid parenchyma and the tumour on the respective sequence. Visual assessment of the nerve is also performed using a three point scale: 2. Whole intraparotid course of the concerned segment/ branch of facial nerve identified with certainty, 1. Partial visualization of the concerned segment/ branch of facial nerve, and 0. Particular branch cannot be identified. The process will be repeated on the DESS, post-contrast CISS and conventional **3D SPACE** sequences for bilateral facial nerves for each patient.

Inter-observer agreement between two observers are calculated using kappa statistics. The measured statistics of subjective and objective conspicuity are evaluated using statistics software (SPSS) using two-way comparison tests (Mann-Whitney U or two-smaples T test) as well as analysis of variance (ANOVA).

Handling and Storage of personal data

Images of usual salivary gland MRI sequences (excluding DESS and CISS sequences) will be uploaded to patient's electronic patient records for clinical use. The research sequences will be stored in the database only, except when the research sequences have impact on clinical management then selected images can be uploaded to ePR for illustration.

All MRI scans will be stored in the picture archiving and communication system of Gerald Choa Neuroscience Center/ Prince of Wales Hospital. These images can be viewed on HA clinical workstations for the purpose of providing clinical care. Radiologist with training in Head and Neck or Neuroradiology will issue a formal radiology report regarding in the examinations, the report will be available on the ePR system.

The MRI data will be anonymized and encrypted before research analysis, which will also be done in HA clinical workstations. MRI scan data after anonymization will be stored in CUHK MRI data repository, with only non-identifiable patient particulars (age, sex, disease status) retained (informed consent obtained from patient prior to scanning). Use of selected images for publication purposes will be anticipated, patient particulars will be removed prior to exporting from HA clinical workstations.

Compliance with Guidelines of Good Clinical Practice by International conference on harmonisation of technical requirements for registration of pharmaceuticals for human use (ICH-GCP) and Declaration of Helsinki

This clinical trial is conducted in accordance with the ethical principles that have their origin in the Declaration of Helsinki, and that are consistent with GCP and the applicable regulatory requirement(s).

This trial offers additional diagnostic benefit without known added clinical risk on top of usual clinical care. The rights, safety, and well-being of the trial subjects are the most important considerations and will be prevailed in the current study. No non-clinical use of product is involved in this study. The radiological examination subjects underwent are provided by qualified medical practitioners with adequate training in radiology.

All clinical trial information should be recorded, handled, and stored in a way that allows its accurate reporting, interpretation and verification.

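### The 80% power behind 42 to 50 patients was computed for DESS against conventional imaging only and does not extend to DESS against CISS, the comparison named first

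*Protocol*

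**What the plan says.** The Protocol's Scientific basis section sets out two comparisons in order. The first is "Our study aim to compare the efficacy between the two sequences", meaning DESS and CISS; the second is introduced by "and also to compare with conventional 3D post-contrast anatomical imaging studies".

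The Patient recruitment section then justifies the size of the study as a whole: "We currently aim to recruit approximately 50 patients for the purpose of the study according to the following basis for calculation of statistical power". The basis consists of two rates, "60% predication of facial nerve with conventional techniques, and ~80% visualization of facial nerves using DESS", and the error rates, "With 80% power and two-tail alpha of 0.05". The result is a minimum of 42 patients.

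The Image interpretation section has DESS, post-contrast CISS and 3D SPACE all read in every patient, on both sides, in eight nerve segments. Each segment is graded 0, 1 or 2 and also measured by signal-intensity ratios. The comparisons named are Mann-Whitney U or two-sample t tests, and analysis of variance.

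Nowhere does the Protocol give a CISS visualisation rate, a DESS-CISS difference, a margin, a target precision or a power for that comparison.

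**The concern.** A reader who is told that the recruitment target serves the purpose of the study, at 80% power, will take that power to cover the study's questions. It was computed for one of them, and that one is listed second. The 20-point gap assumed between DESS and conventional imaging says nothing about the gap between DESS and CISS. The Scientific basis section reports both as showing the nerve better, and calls their relative advantages unknown.

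What is at stake is how a DESS-CISS result can be used. For the comparisons the Protocol names tests but no estimate or interval. If the test is non-significant, readers need to know which differences the study could have missed, and the sample-size paragraph gives them a power figure that belongs to another comparison.

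**Working it through.** **Inputs from the Protocol.** Conventional about 60%, DESS about 80%, power 80%, two-sided alpha 0.05, minimum 42, target about 50 (Patient recruitment); 8 segments on 2 sides, so 16 per patient per sequence, with all sequences in the same patient (Image interpretation).

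**Assumptions, because the Protocol gives no figure.** The CISS rate; the proportion of discordant pairs π between DESS and CISS; the within-patient correlation of segment differences (ICC). Results are shown as ranges.

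**1. Reproducing 42.** A one-sample test of 80% against a fixed 60% gives

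n = (1.960·√(0.6·0.4) + 0.842·√(0.8·0.2))² / 0.20² = (0.960 + 0.337)² / 0.04 = 42.04.

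This matches the stated 42 (43 if rounded up) and uses no CISS input. Other routes for the same two rates:
- Paired (McNemar) test: 41 pairs at 22% discordance, 45 at 24%. The minimum possible discordance for a 20-point gap is 20%.
- Two independent samples: 82 per group. With 50 readings per sequence, power = Φ[(0.2·√50 − 1.960·√(2·0.7·0.3)) / √(0.24 + 0.16)] = Φ(0.228) = 59%.

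**2. DESS against CISS, one yes/no result per patient, n = 50.** For a paired difference d, power = Φ[(d·√n − 1.960·√π) / √(π − d²)]. Take d = 0.10 and DESS at 80%.
- Minimum discordance, π = 0.10: Φ[(0.707 − 0.620) / 0.300] = 61%.
- CISS 90%, readings independent, π = 0.8·0.1 + 0.2·0.9 = 0.26: 28%.
- CISS 70%, readings independent, π = 0.8·0.3 + 0.2·0.7 = 0.38: Φ[(0.707 − 1.208) / 0.608] = 21%.

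The range is therefore 21% to 61%, from minimum discordance to independence.

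**3. Segments as unit.** There are 16 × 50 = 800 segments per sequence. The design effect is 1 + 15·ICC and the effective number is 800 divided by it. Each segment is treated as yes/no, which simplifies the three-point grade. Discordance is taken as 20% to 32%; 32% is independence at 80% for both sequences (2·0.8·0.2). The half-width is 1.96·√(π / effective number), for an observed difference near zero.

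| ICC | Design effect | Effective number | Power for 10 points (π 0.20 to 0.32) | 95% CI half-width (π 0.20 to 0.32) |
|---|---|---|---|---|
| 0.1 | 2.5 | 320 | 98% to 89% | 4.9 to 6.2 points |
| 0.2 | 4.0 | 200 | 89% to 71% | 6.2 to 7.8 points |
| 0.5 | 8.5 | 94 | 59% to 40% | 9.0 to 11.4 points |

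If discordance were at its floor of 10%, power at ICC 0.5 would be 88%. Power of 80% therefore needs low clustering or low discordance, and the Protocol assumes neither.

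**4. Precision with one result per patient, n = 50.** Half-width 1.96·√(π/50): 8.8 points at π = 0.10, 12.4 at 0.20, 15.7 at 0.32.

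**The case against.** The strongest reply is that one yes/no result per patient is not what the study measures. Sixteen graded segments and continuous ratios per patient carry more information, and the half-width then falls to about 5 to 11 points. This stands. It rules out saying that only very large differences could be detected, or that a null DESS-CISS result will be uninformative. A reader might infer either from the patient-level figures, but even those would exclude differences beyond about 9 to 16 points if the observed difference were near zero. The sample-size paragraph nevertheless counts patients and states no clustering, so it cannot claim the gain from segments.

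A second reply is that no comparison is designated primary, that sizing on one comparison is common, and that both input rates are printed openly. This also stands in part. First place in the aim is word order only, and the Protocol nowhere explicitly claims power for DESS against CISS. But the paragraph attaches its basis to the study's whole purpose without limiting it.

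A third is that intervals and interpretation rules may sit in an analysis plan that is not shown, and that no equivalence claim appears in the Protocol. Both are true. The finding is the reach of the power statement, which the Protocol itself makes; the reporting advice follows from it. It does not assume that anyone intends to claim equivalence.

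**Conclusion.** The point holds in a limited form. The stated 80% power and the 42 to 50 patients rest on DESS against conventional imaging alone and do not extend to DESS against CISS. Power for that comparison is unknown. For 10 points at 50 patients it is about 21% to 61% with the patient as unit. On segments it is about 40% to 98% for ICC 0.5 down to 0.1 and discordance of 20% to 32%. A non-significant result may leave a difference of about 10 points open and is not evidence of equivalence.

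These ranges rest on assumed CISS rates, discordance and ICC, and on yes/no outcomes; the signal-intensity ratios were not assessed. A reader might go further and conclude that the study is too small for its first aim. The documents do not support that: they give no relevant DESS-CISS difference to size against, and a segment analysis with low clustering could be adequate.

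Nor should 42 be taken as sound for the tests that are named. It fits a fixed 60% benchmark or a paired test near minimum discordance, whereas two-sample tests with 50 readings per sequence give about 59% power.

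**What to change.** In the Patient recruitment section:
- State that the 80% power refers to DESS against conventional imaging only, and give the test and unit from which 42 was derived.
- State that DESS against CISS was not separately sized.
- Give the expected precision for DESS against CISS as a range with its assumptions: for example, a 95% confidence interval half-width of about 5 to 11 points on segments (ICC 0.1 to 0.5, discordance 20% to 32%), or about 9 to 16 points with one result per patient (discordance 10% to 32%).

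In the Image interpretation section, or in the analysis plan if one exists:
- Report DESS against CISS as a within-patient paired difference with a 95% confidence interval that allows for clustering of segments.
- State that non-significance will not be read as equivalence.

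The cost is a few sentences and a paired, clustered analysis in place of a bare two-sample test. No extra patients or scans are needed. The drawback is a less favourable statement of power for the first aim.

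### The stated 80% power with 42 patients fits a one-sample test of 80% against a fixed 60%, not any comparison the protocol plans

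*Protocol*

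**What the plan says.** **Sizing (Study protocol, Patient recruitment).** The recruitment target is "We currently aim to recruit approximately 50 patients for the purpose of the study". Its basis is two rates from previous studies: "there is an estimated ~60% predication of facial nerve with conventional techniques, and ~80% visualization of facial nerves using DESS". The result is: "With 80% power and two-tail alpha of 0.05, at least 42 patients will be needed according to sample size calculation". The formula is not given. Nor is it said whether the rates apply per segment or per patient.

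**Outcomes and tests (Image interpretation).** Each facial nerve is divided into eight segments, read on both sides and on three sequences: DESS, post-contrast CISS and conventional 3D SPACE. Each segment gets a signal-intensity ratio and an ordinal score: "Visual assessment of the nerve is also performed using a three point scale". On that scale 2 means the whole course is identified, 0 means it is not identified, and 1 is "Partial visualization of the concerned segment/ branch of facial nerve". For the analysis, "The measured statistics of subjective and objective conspicuity are evaluated using statistics software (SPSS) using two-way comparison tests", namely Mann-Whitney U or a two-sample t test, and also ANOVA.

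**The concern.** The sizing paragraph speaks of a rate of visualisation. The analysis paragraph speaks of scores and ratios. Three links between them are missing:

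- which scores count as visualised, and in particular whether a partial view does;
- whether the rate is per segment or per patient, when each patient has 8 × 2 = 16 scored segments on each sequence;
- any test of proportions.

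A further mismatch shows once the number is reproduced. It treats the conventional rate as a known constant, although this trial estimates that rate in its own patients.

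The power statement is the only justification for the number recruited. If it belongs to a different test, the reader does not know what the trial can detect on the comparison it will report.

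**Working it through.** **Inputs from the protocol:** 60% conventional, 80% DESS, two-sided alpha 0.05, power 80%, minimum 42, target about 50. Normal quantiles: 1.960 and 0.842.

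**Assumptions of this check:** one yes/no result per patient per sequence, and a within-patient correlation (phi) between sequences of 0 to 0.5. The protocol gives no correlation.

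**1. Reproducing 42.** One-sample test of 80% against a fixed 60%:

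n = (1.960·√(0.6·0.4) + 0.842·√(0.8·0.2))² / 0.2² = (1.2968)² / 0.04 = **42.04**

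Power at n = 42 is 79.95%. The stated figure is therefore correct for this test.

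**2. Unpaired comparison of 60% v 80%.**

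n per group = (1.960·√(2·0.7·0.3) + 0.842·√(0.24 + 0.16))² / 0.2² = 81.2, so **82 per group**

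With 42 readings per sequence power is **52%**; with 50 it is **59%**.

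**3. Paired comparison (McNemar), same rates.** With phi, the share positive on both sequences is 0.48 + phi·√(0.24·0.16). The discordant share is D = 0.44 − 2·phi·0.196, and the difference is d = 0.20.

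n = (1.960·√D + 0.842·√(D − d²))² / d²

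power = Φ[(d·√n − 1.960·√D) / √(D − d²)]

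| phi | D | n for 80% | power, 42 patients | power, 50 patients |
|---|---|---|---|---|
| 0 | 0.440 | 84 | 50% | 57% |
| 0.3 | 0.322 | 61 | 63% | 71% |
| 0.5 | 0.244 | 46 | 77% | 84% |

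This test also gives 42, but only if D is about 0.23, close to the smallest value that 60% and 80% allow (0.20). At that limit 37 patients suffice, and power is 85% with 42 and 91% with 50. The protocol states no discordance, so nothing indicates that this was the calculation.

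**4. The Mann-Whitney test that is named.** As an illustration, power was simulated for five assumed pairs of 0/1/2 distributions, each consistent with 60% v 80% under one reading of visualised. One score per patient was used and sequences were treated as independent, as that test does.

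- Lowest: conventional 40/30/30% v DESS 20/50/30% (scores 0/1/2), where the whole gain is in partial views. Power was about 23% with 42 and 25% with 50.
- Highest: conventional 40/30/30% v DESS 20/26.7/53.3%. Power was about 67% with 42 and 75% with 50.

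The same pair of rates thus gives very different power, depending on how the score moves.

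**The case against.** **Visualisation is scored.** A reader might infer that the trial never records the quantity it was sized on. The documents do not support that: a yes/no rate can be derived from the scale, as score 2 or as score 1 or 2. Sizing on a dichotomised scale and then analysing the full scale is a common simplification, and on a two-level score Mann-Whitney is essentially the two-proportion test. This stands, and it limits the point to the missing link. It does not rescue the 80%, because the two-proportion test needs about 82 per group, not 42.

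**The number is not an arithmetic slip.** It is right for a one-sample test. The trouble is that the trial compares two sequences, both read in its own patients.

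**Detail may sit in an unseen SAP.** A cut-point, a rule for combining segments and the choice of primary measure are often left there, and their absence alone would be no finding. But the protocol itself states both the power and the tests, and these do not match.

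**The trial may still have enough power.** The paired range with 50 patients includes 80%, and using all 16 segments per patient with a clustered method could raise power. Part of the Mann-Whitney shortfall comes from ignoring the pairing, which is a separate matter from the endpoint. These objections stand.

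**Wording.** The differing terms for the two rates (predication, visualization) may be a language slip and carry no weight here.

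**Conclusion.** The point holds in a limited form. The stated 80% power cannot be attached to the comparison the protocol plans, because 42 matches a one-sample test against a fixed 60% and the planned tests are of another kind on other quantities.

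At the protocol's own 60% v 80%, with one paired yes/no result per patient and an assumed correlation of 0 to 0.5, power is about 50-77% with 42 patients and 57-84% with 50. Unpaired, it is about 52% and 59%. These figures rest on the assumed correlation and on one result per patient.

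Two stronger readings go too far. One is that the trial is certainly underpowered: the documents give neither the correlation nor the unit needed to say so. The other is that success will be claimed on whichever measure favours DESS: the protocol states no success criterion from which that follows.

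This should be corrected, but it does not undermine the data to be collected.

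**What to change.** Before the images are analysed, name one primary comparison of DESS with 3D SPACE. Either choice would do:

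- **A visualised proportion**, with the cut-point (score 2, or score 1 or 2) and the unit (segment or patient) stated. Test it with McNemar for one result per patient, or with a logistic GEE clustered on patient over the segments.
- **The 0/1/2 score**, with a paired or clustered ordinal method.

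Then restate the power of about 50 patients for that comparison, showing the assumed within-patient correlation and a range around it. Report the signal ratios and the other sequence pairs as secondary.

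The cost is protocol wording, one recalculation and one routine analysis, with no new patients, scans or readings. The downside is that the restated power may fall below 80%, and the protocol would have to say so. A cut-point chosen after the readings are compared would carry less weight, so the timing matters.

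### All sequences are read on both facial nerves of every patient, but the pairwise tests named assume independent samples and the 80% power is not determined by the inputs given

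*Protocol*

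**What the plan says.** The Patient recruitment section gives the planning rates: "there is an estimated ~60% predication of facial nerve with conventional techniques, and ~80% visualization of facial nerves using DESS". It then states: "With 80% power and two-tail alpha of 0.05, at least 42 patients will be needed according to sample size calculation". The target is tied to that calculation: "We currently aim to recruit approximately 50 patients for the purpose of the study according to the following basis for calculation of statistical power". No discordance between sequences and no within-patient correlation is given.

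The Scientific basis section makes conventional imaging a comparator; the study is "also to compare with conventional 3D post-contrast anatomical imaging studies in the localization and visualization of the facial nerve branches".

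The Image interpretation section sets out the readings. "The intra-parotid facial nerve will be segmented into eight segments", and "Visual assessment of the nerve is also performed using a three point scale", alongside a signal-intensity ratio. "The process will be repeated on the DESS, post-contrast CISS and conventional" 3D SPACE "sequences for bilateral facial nerves for each patient". For the analysis it names Mann-Whitney U or a two-sample t test as the two-way comparisons, and also ANOVA, without saying whether the ANOVA is for repeated measures.

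**The concern.** Each patient contributes a reading on every sequence and on both sides. Any comparison between sequences is therefore within patient, with two nerves clustered in each. Mann-Whitney U and the two-sample t test treat the two sets of readings as coming from different, unrelated subjects. That discards the pairing, which is the design's main strength, and ignores the correlation between a patient's two sides.

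The power sentence has the same gap. Two marginal rates fix the power of a comparison between independent groups, but not of a paired and clustered one.

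Two things are at stake. The p-values and confidence intervals for the main comparison would be wrong if the section is followed as written. And a null result for DESS against conventional imaging would be read as coming from a study with 80% power, when power could lie well above or below that.

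**Working it through.** **1. The named tests.** Let ρ be the correlation between two sequences on the same nerve, ICC the side-to-side correlation of the paired difference, σ² the variance of a reading and n the number of patients. The documents give none of these correlations, so every value below is an assumption.

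An independent-samples test with m readings per sequence uses variance 2σ²/m for the difference in means. The true variance is:
- one reading per patient (m = n): 2σ²(1 − ρ)/n, so true/assumed = 1 − ρ;
- both sides pooled (m = 2n): 2σ²(1 − ρ)(1 + ICC)/(2n), so true/assumed = (1 − ρ)(1 + ICC).

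The actual two-sided error rate at nominal 5% is about 2Φ(−1.96/√ratio):

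| ρ | ICC | ratio | actual type I error |
|---|---|---|---|
| 0.5 | one reading | 0.50 | 0.6% |
| 0.5 | 0.3 | 0.5 × 1.3 = 0.65 | 1.5% |
| 0.1 | 0.3 | 0.9 × 1.3 = 1.17 | 7.0% |

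The error can go either way. With clearly positive ρ the test is too conservative. For 50 pairs, one reading each, ρ = 0.5 and a shift of 0.4 SD, the true standard error is √(2 × 0.5/50) = 0.141 SD, and 0.4/0.141 = 2.83. The paired t test needs about 2.01. The two-sample t test in effect needs 1.98 × √2 = 2.81. Simulated power is about 79% paired and 51% unpaired.

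**2. Where 42 can come from.** Inputs from Patient recruitment: 0.60, 0.80, two-sided alpha 0.05 (1.96), power 80% (0.8416), difference 0.20.

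- One-sample test against a fixed 60%: (1.96√0.24 + 0.8416√0.16)²/0.04 = (0.960 + 0.337)²/0.04 = 42.04. This matches, but the trial measures the conventional sequence in the same patients.
- Paired comparison: n = (1.96√pd + 0.8416√(pd − 0.04))²/0.04, where pd is the share of nerves seen on only one of the two sequences. If the sequences are uncorrelated, pd = 0.6 × 0.2 + 0.4 × 0.8 = 0.44 and n = (1.300 + 0.532)²/0.04 = 83.9, that is 84 nerves. Over two sides this is 42 patients, provided the sides are independent.
- Two independent groups: 82 per group. Counted as nerves and halved this is 41, close but not 42.

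The document does not settle which route was used.

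**3. Power once pairing and sides are allowed for.** The margins 60% and 80% allow pd from 0.20 (no nerve seen only on the conventional sequence) upward; 0.44 is no correlation between sequences. The test simulated is a clustered McNemar, z = Σs/√Σs², where s is the patient's sum of paired differences over the two sides.

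| Patients | pd | ICC 0 | ICC 0.3 | ICC 0.5 |
|---|---|---|---|---|
| 42 | 0.20 | >99% | >99% | >99% |
| 42 | 0.30 | 95% | 88% | 83% |
| 42 | 0.44 | 80% | 69% | 63% |
| 50 | 0.20 | >99% | >99% | >99% |
| 50 | 0.30 | 98% | 93% | 89% |
| 50 | 0.44 | 87% | 77% | 71% |

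The closed form at effective size 2n/(1 + ICC) is within about 4 points at pd 0.30 and 0.44. At pd 0.20 it is lower: 94–99% at 42 patients and 97% or more at 50. The eight segments and the two readers are not modelled.

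**The case against.** The strongest reply is that 42 is reproducible by a route that uses the protocol's own bilateral, paired layout, and that its assumption of uncorrelated sequences is pessimistic: two sequences reading the same nerve would normally agree more than by chance, which lowers discordance and raises power. The plan also recruits about 50, 19% above the stated minimum (50/42 = 1.19). By the closed form, 50 patients keep 80% up to a discordance of about 0.40 at ICC 0.3, and about 0.35 at ICC 0.5. All of this stands. The same route also takes the two sides as independent, which is favourable, and neither assumption is written down.

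A reader might infer that the trial is underpowered, or that 42 is a miscalculation. The documents support neither. Low figures, such as 42% at 42 patients and 50% at 50 (exact McNemar, discordance 0.44), arise only if each patient supplies a single binary reading, whereas the protocol reads both nerves.

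A reader might also count the missing cut-point on the three-point scale and the unnamed unit of analysis as separate defects. A statistical analysis plan, not shown here, may supply them.

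On the tests, the protocol does not say outright that the two-sample tests serve the between-sequence contrasts, and its ANOVA may be a repeated-measures one. But comparing sequences is the stated aim, and these are the only pairwise tests named for the conspicuity measures. Taking conventional techniques in the sample size paragraph to mean the 3D SPACE sequence is likewise an inference from the Scientific basis and Image interpretation sections.

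**Conclusion.** The point holds in two parts, and both should be fixed. First, the pairwise tests named do not fit the design. Followed as written, they give wrong error bars: too wide when sequences are clearly positively correlated (type I error about 0.6% and power 51% against 79% in the example), and possibly too narrow when that correlation is weak and the two sides are correlated. Second, the unconditional 80% power is not determined by the inputs stated. It is an unsupported figure, not an arithmetic error, and no shortfall is shown. Over assumed discordance 0.20, 0.30 and 0.44 and ICC 0 to 0.5, power is above 99%, 83–95% and 63–80% at 42 patients, and above 99%, 89–98% and 71–87% at 50. These ranges rest on assumed discordance and ICC, on both sides being analysed, and on a binary visualisation outcome at 60% and 80%.

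**What to change.** **Image interpretation.** For comparisons between sequences, replace Mann-Whitney U and the two-sample t test with paired or repeated-measures methods that treat the patient as the cluster. Options are a clustered signed-rank test or ordinal GEE for the three-point score, a mixed model for the signal ratio, and a clustered McNemar test if the score is dichotomised. If ANOVA is kept, say that it is for repeated measures.

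**Patient recruitment.** Replace the unconditional 80% with a conditional statement that names the unit. For example: *With both facial nerves read in about 50 patients (nerve as unit, patient as cluster), a clustered McNemar test of 60% against 80% at two-sided alpha 0.05 has power above 99%, 89–98% and 71–87% at assumed discordance of 0.20, 0.30 and 0.44, the ranges covering an assumed side-to-side ICC of 0 to 0.5.* Fixing one ICC value would only swap one unsupported figure for another, so the range should stay. If the sponsor has data on discordance or side-to-side correlation, those should replace the assumptions.

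**Cost.** Two passages of text. Recruitment, scanning and reading do not change. The stated power becomes conditional and may fall below 80% in the unfavourable cases.
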